5.5.3 Secondary Efficacy Endpoints

5.5.3.1 Key Secondary Efficacy Endpoints

5.5.3.1.1 1st Key Secondary Endpoint: TSC-associated Seizure Treatment

Responders (≥50% Reduction in TSC-associated Seizure Frequency)

Blinded Phase:

The proportion of patients considered treatment responders, defined as those with a $\geq 50\%$ reduction in TSC-associated seizure frequency from baseline during the treatment period, for patients who have not withdrawn from the trial during the treatment period, will be summarized by treatment arm and analyzed using a Cochran–Mantel–Haenszel (CMH) test stratified by age group.

The proportion of patients who are considered treatment responders, the difference in proportions along with the 95% CI for the difference, the estimated odds ratios (GWP42003-P arms vs. placebo), 95% CI for the odds ratios, and the p-values from the CMH test will be presented. If no patients in a particular treatment arm are considered responders then the odds ratio and 95% CI for the odds ratio will not be calculated.

The analysis will be performed on the ITT analysis set and repeated on the PP analysis set.

Sensitivity analyses will be performed on the ITT analysis set, repeating the above analysis, using data for the maintenance period only, the titration period and during each 4 weeks of the maintenance period (Week 1 to 4, Week 5 to 8 and Week 9 to 12 of the 12 week maintenance period).

Analyses on the maintenance period, titration period and by each 4 weeks of the maintenance period will include only patients who have at least 7 days of seizure data within each period.

Open-label Extension:

Descriptive summaries described above for the blinded phase will be repeated for OLE periods. However, for the OLE periods, withdrawn patients may be considered responders.

5.5.3.1.2 2nd Key Secondary Endpoint: Subject/Caregiver Global Impression of Change

Blinded Phase:

The SGIC and CGIC comprise the following questions to be rated on a 7-point scale:

CGIC:

- Since your child started treatment, please assess the status of your child's overall condition (comparing their condition now to their condition before treatment) using the scale below.

SGIC:

- Since you started treatment, please assess the status of your overall condition (comparing your condition now to your condition before treatment) using the scale below.

The possible responses are: Very Much Improved; Much Improved; Slightly Improved; No Change; Slightly Worse; Much Worse; Very Much Worse.

The responses above are based on comparison with a brief description of the patient's overall condition used as a memory aid from Visit 3.

Each response will be coded with a score from 1 to 7, where 1 = Very Much Improved, and 7 = Very Much Worse.

The SGIC and CGIC response/score, recorded at each visit, will be summarized separately, on both a categorical and continuous scale, by treatment arm.

It is anticipated that only a small percentage of patients will complete the subject version of the questionnaire. Hence, no analyses will be performed for the SGIC.

A combined score will be used as the primary analysis for this endpoint. The combined score will be defined as follows:

- If both a CGIC and SGIC are completed then the CGIC will be used.
- If only a CGIC is completed then the CGIC will be used.
- If only a SGIC is completed then the SGIC will be used.

The score at the end of treatment visit and last visit (if different to the end of treatment) will be analyzed using ordinal logistic regression. Proportional odds modelling will be carried out by including treatment arm as a factor. The estimated odds ratio (GWP42003-P vs. placebo), 95% CI for the odds ratio, and the p-value testing the null hypothesis that the odds ratio is equal to 1, will be presented. Analysis performed at the last visit will be considered the primary analysis for this endpoint, with the analysis at the end of treatment visit considered a sensitivity analysis.

Should the proportional odds assumption not hold, i.e. if the p-value for the score test for proportional odds assumption is <0.05 , then, as a sensitivity analysis, the scores will also be analyzed using a Cochran-Armitage trend test. This will be presented together with the results of the ordinal logistic regression.

Since this analysis uses a combination of caregiver and subject ratings, a sensitivity analysis will be performed using only the CGIC score and using the same analyses as above.

The analysis will be performed on the ITT analysis set and repeated on the PP analysis set.

Open-label Extension:

Descriptive summaries described above for the blinded phase will be repeated for OLE visits.

5.5.3.1.3 3rd Key Secondary Endpoint: Total Seizures

Blinded Phase:

Summaries and analyses of total seizures (see Section 5.1.3.9) will be performed as per the primary endpoint (Section 5.5.2).

The analysis will be performed on the ITT analysis set and repeated on the PP analysis set.

Sensitivity analyses will be performed on the ITT analysis set, repeating the above analysis, using data for only the maintenance period, titration period, and during each 4 weeks of the maintenance period (Week 1 to 4, Week 5 to 8 and Week 9 to 12 of the 12 week maintenance period).

Analyses on the maintenance period, titration period and by each 4 weeks of the maintenance period will include only patients who have at least 7 days of seizure data within each period.

Open-label Extension:

Summaries will be performed for the OLE periods as described in the OLE portion of the primary endpoint section (Section 5.5.2).

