#### **Blinded Phase:**

The number of patient responders (including the key secondary endpoint) and the number of patients seizure-free will be summarized and analyzed using a Cochran–Mantel–Haenszel test stratified by age group. In addition, the difference in proportions and the odds ratio, together with 95% CIs, comparing the treatment groups will be presented.

For number of seizure-free days, use of rescue medication, number of episodes of *status epilepticus* (only if there is a sufficient number of patients with data), Vineland-II, Wechsler scales, CBCL, ABCL, SCQ, QOLCE and QOLIE-31-P scores, the data will be summarized at baseline and over the treatment period, and at each time-point (or 28-day period, as appropriate) during the maintenance period. Changes from baseline to the average over the treatment period (or at end of study) will be analyzed using ANCOVA (or appropriate non-parametric methods if data are found to be not normally distributed). The models will include baseline and age group as covariates and treatment group as fixed factor. The treatment difference, together with the 95% CIs will be presented.

The changes in composite focal seizure score, change in total seizures, the number of seizures by subtype and the number of 'other' seizures will be analyzed using the same analysis as the primary endpoint.

SGIC-SD/CGIC-SD, SGIC/CGIC and PGIC assessments recorded at the end of treatment will be analyzed with ordinal logistic regression using the proportional odds model.

Changes from baseline for IGF-1 levels will be summarized by treatment group and plotted against the Tanner Stages, weight, and height.

Tanner Stages will be evaluated and summarized descriptively at each time-point in terms of frequency and proportions. Number (%) of patients with changes in Tanner Stages will be summarized by treatment group.

In order to explore the robustness of the primary analysis, further sensitivity analysis (in addition to that already detailed in Section 13.6.2.1) may be specified in the SAP.

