3. INVESTIGATIONAL PLAN

3.1 Trial Design

This multicenter trial consists of a randomized, placebo-controlled, double-blind phase followed by an open-label extension (OLE) phase.

Blinded Phase:

The blinded phase of the trial is a randomized, double-blind, parallel-group, 16-week comparison of two doses of GWP42003-P vs. placebo. Patients will complete a 1-week screening period and a 4-week baseline period before they are randomized to receive either 25 mg/kg/day GWP42003-P, 50 mg/kg/day GWP42003 P or placebo. Randomization will be stratified by age according to the following ranges: 1–6, 7–11, 12–17 years and 18–65 years. Patients will begin a 4-week dose escalation period, titrating up to their assigned dose, before continuing on a stable dose of blinded Investigational Medicinal Product (IMP) for 12 weeks.

Dose escalation for each patient is subject to the investigator's assessment of safety and tolerability. If a dose becomes poorly tolerated, the investigator may consider temporarily or permanently reducing the dose for the remainder of the trial.

Following completion of the blinded phase, patients will be invited to continue to receive GWP42003-P in an OLE.

Those patients opting not to enter the OLE will complete a 10-day taper period (down-titrating 10% per day for 10 days).

Open-label Extension Transition:

In order to maintain consistent exposure to IMP and maintain the integrity of the blind, patients will enter a 2-week blinded transition to the OLE. OLE IMP will be titrated up to 25 mg/kg/day whilst blinded IMP is simultaneously tapered down to zero. All patients will complete the transition and enter the OLE taking 25 mg/kg/day GWP42003-P:

- Patients from the placebo arm will titrate up to 25 mg/kg/day GWP42003-P.
- Patients from the 25 mg/kg/day GWP42003-P arm will continue to take 25 mg/kg/day GWP42003-P.
- Patients from the 50 mg/kg/day GWP42003-P arm will taper down (10% per day) to 25 mg/kg/day GWP42003-P.

Open-label Extension:

The OLE consists of a 3-week titration period followed by a maintenance period and a 10-day taper period. The initial OLE period will last for a maximum of 1 year.

Following titration according to the titration schedule, patients will continue with their optimal GWP42003-P dose. However, investigators may decrease the dose if a patient experiences intolerance, or increase the dose to a maximum of 50 mg/kg/day if required for better seizure control, until the optimal dose is found.

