3.2 Definition of Sample Size

Blinded Phase:

A total of 210 patients will be enrolled. The 210 patients will be randomly allocated to 1 of 4 treatment arms (GWP42003-P 25 mg/kg/day, GWP42003 P 50 mg/kg/day, placebo 25 mg/kg/day dose volume equivalent, or placebo 50 mg/kg/day dose volume equivalent) at a 2:2:1:1 ratio. The placebo arms will be pooled for the analyses of efficacy.

If it is assumed that patients in the placebo arm will experience a mean reduction in seizure frequency of 15% (from baseline), patients receiving GWP42003-P will experience at least a 50% reduction in seizures and a common standard deviation of 60%, then this sample size of 70 patients per arm will be sufficient to detect a difference in response distributions with 90% power. This test is based on a two-sided non-parametric Mann-Whitney-Wilcoxon test for continuous response data with a 5% significance level.

Open-label Extension:

All patients who wish to continue on IMP following the blinded phase.

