5.5 Efficacy Analysis

5.5.1 General Approach

Blinded Phase:

The primary analyses will use the ITT analysis set. Further analyses using the PP analysis set will also be performed for the primary endpoint and secondary endpoints where specified in the sections below.

The primary null hypothesis is:

- Following 16 weeks of treatment there is no difference in effect between the 25 mg/kg/day GWP42003-P treatment arm and the placebo treatment arm in terms of the change in number of TSC-associated seizures during the treatment period compared to baseline.

The null hypothesis will be rejected if there is statistical evidence of a difference between the treatment arms at the α -level of 0.05 for the primary endpoint.

Statistical hypothesis testing will be performed on the primary endpoint and other endpoints as appropriate. Each endpoint, including the primary will have 2 comparisons against placebo (25 mg/kg/day GWP42003-P vs. placebo and 50 mg/kg/day GWP42003-P vs. placebo). Also, 3 key secondary endpoints have been defined.

The primary and key secondary endpoints will be tested with their Type I error controlled by use of a hierarchical gate-keeping procedure, in the sequence given in Table 3. One must reject the null hypothesis of an endpoint at the level of 0.05 (2-sided) to test the hypothesis of the subsequent endpoint in the sequence at the level of 0.05 (2-sided). If a null hypothesis is not rejected then testing will stop and all subsequent analyses will be declared not statistically significant.

Table 3 Hierarchy for Analysis

Test	Endpoint	Treatment Comparison
1	Primary endpoint	25 mg/kg/day GWP42003-P vs. Placebo
2	1 st key secondary endpoint	25 mg/kg/day GWP42003-P vs. Placebo
3	Primary endpoint	50 mg/kg/day GWP42003-P vs. Placebo
4	1 st key secondary endpoint	50 mg/kg/day GWP42003-P vs. Placebo
5	2 nd key secondary endpoint	25 mg/kg/day GWP42003-P vs. Placebo

6	3 rd key secondary endpoint	25 mg/kg/day GWP42003-P vs. Placebo
7	2 nd key secondary endpoint	50 mg/kg/day GWP42003-P vs. Placebo
8	3 rd key secondary endpoint	50 mg/kg/day GWP42003-P vs. Placebo

All statistical tests will be 2-sided and use the 5% significance level.

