5.5.4.5 Subject/Caregiver Global Impression of Change in Seizure Duration

Blinded Phase:

The SGICSD and CGICSD comprise the following questions to be rated on a 3-point scale for each seizure type:

CGICSD:

- Since the patient started treatment, please assess the average duration of the patient's seizures (comparing their condition now to their condition before treatment) using the scale below.

SGICSD:

- Since you started treatment, please assess the average duration of your seizures (comparing your condition now to your condition before treatment) using the scale below.

The 3 possible responses are:

- Decrease in average duration.
- No change in average duration.
- Increase in average duration.

The patient/caregiver will be asked to assess the average duration of seizures at Visit 3 (prior to commencement of IMP) as a memory aid for assessment further visits.

Each response will be coded with a score from 1 to 3, where 1 = Decrease in average duration, and 3 = Increase in average duration.

For each seizure type, the SGICSD and CGICSD will be summarized separately by treatment arm.

It is anticipated that only a small percentage of patients will complete the subject version of the questionnaire. Hence, no analyses will be performed for the SGICSD.

A combined score will be used as the primary analysis for this endpoint. The combined score will be defined as follows:

- If both a CGICSD and SGICSD are completed then the CGICSD will be used.
- If only a CGICSD is completed then the CGICSD will be used.
- If only a SGICSD is completed then the SGICSD will be used.

Proportional odd modelling will be carried out by including treatment arm and age group as factors. The estimated odds ratio (GWP42003-P vs. placebo), 95% CI for the odds ratio, and the p-value testing the null hypothesis that the odds ratio is equal to 1, will be presented.

Since this analysis uses a combination of caregiver and subject ratings, a sensitivity analysis will be performed using only the CGICSD score and using the same analyses as above.

Open-label Extension:

Descriptive summaries described above for the blinded phase will be repeated for OLE visits.

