Clinically Significant	21 to 24	
Elevated	18 to 20	
Average	1 to 17	

The v-scale score from the 11 adaptive behavior subdomains, 3 maladaptive behavior subdomains and the maladaptive behavior index, and the standard score from the 4 adaptive behavior domains and the adaptive behavior composite, recorded at each visit, will be summarized, on a continuous scale, by treatment arm. The change from baseline will also be included.

The change from baseline to the end of treatment visit, for the 4 adaptive behavior domains, the adaptive behavior composite and the maladaptive behavior index only, will be analyzed using the same ANCOVA approach as specified in Section 5.5.3.2.4.

The adaptive level from the 11 adaptive behavior subdomains, 4 adaptive behavior domains, the adaptive behavior composite, the 3 maladaptive behavior subdomains and the maladaptive behavior index, recorded at each visit, will be summarized, on a categorical scale, by treatment arm.

The adaptive level from the 4 adaptive behavior domains, the adaptive behavior composite and the maladaptive behavior index only will be analyzed using ordinal logistic regression. Factors for treatment and age group will be included along with the baseline adaptive level as a covariate. The estimated odds ratios (GWP42003-P arms vs. placebo), 95% CI for the odds ratios, and the p-values testing the null hypothesis that the odds ratio is equal to 1, will be presented.

Each adaptive level for adaptive behavior will be coded with a score from 1 to 5, where 1 = Low, and 5 = High. Each adaptive level for the maladaptive behavior index will be coded with a score from 1 to 3, where 1 = Clinically Significant, and 3 = Average.

The individual responses within each domain will not be listed, only the derived information for each subdomain and domain will be listed.

Open-label Extension:

Descriptive summaries described above for the blinded phase will be repeated for OLE visits.

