5.5.5 Subgroup Analyses

To assess the degree of effect heterogeneity, effect modifier analyses are proposed, on the ITT analysis set, for the primary efficacy endpoint and the key secondary efficacy endpoint of $\geq 50\%$ reduction in TSC-associated seizure frequency.

For the primary efficacy endpoint, the effect modifier analysis will be performed using the negative binomial regression analysis as described in Section 5.5.2. The model will be updated to include covariates for each level of the effect being tested (excluding a reference level), individually and with interactions with time, interactions with treatment arm and interactions with time and treatment. A separate model will be used for testing each effect. The treatment ratios (GWP42003-P vs. placebo), percent reduction and 95% confidence intervals will be presented for each level of the effect. In addition, the effect by time by treatment arm interaction p-value, testing the hypothesis that the effect level treatment ratios are homogeneous, will be presented.

For the key secondary efficacy endpoint of $\geq 50\%$ reduction in TSC-associated seizure frequency, patients with a $\geq 50\%$ reduction in seizure frequency will be modelled using logistic regression, including stratified age group and treatment arm as covariates. The model will also include covariates for each level of the effect being tested (excluding a reference level), individually and with interactions with treatment arm. A separate model will be used for testing each effect. The number and percent of responders, and odds ratios and 95% confidence intervals will be presented for each level of the effect. In addition, the effect by treatment arm interaction p-value, testing the hypothesis that the effect level odds ratios are homogeneous, will be presented.

The following effects will be tested:

- Age group (1-6 years, 7-11 years, 12-17 years and 18-65 years). Note: stratified age group will be removed as a covariate for this model.
- Sex (Male, Female).
- Region (US, Rest of the World).
- Clobazam use (Yes, No).
- Valproic acid use (Yes, No).
- Levetiracetam use (Yes, No).
- Vigabatrin use (Yes, No).
- Baseline average TSC-associated seizures per 28 days (\leq observed Tertile 1, $>$ observed Tertile 1 to \leq observed Tertile 2, $>$ observed Tertile 2). The observed tertile values will be rounded to the nearest whole number.
- Number of concurrent AEDs (<3 , ≥ 3).
- Number of prior AEDs (<5 , ≥ 5).

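### The alpha-controlled CGIC/SGIC model (tests 5 and 7) omits the age strata used to randomize; if age is prognostic, the test is conservative and loses power

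*SAP*

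**What the plan says.** SAP 3.1 states: "Randomization will be stratified by age according to the following ranges", followed by 1–6, 7–11, 12–17 and 18–65 years. Protocol 7.2 gives the same four strata.

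For the second key secondary endpoint, the combined caregiver/subject global impression of change, SAP 5.5.3.1.2 says: "Proportional odds modelling will be carried out by including treatment arm as a factor". No other term is named. The last-visit analysis is primary for this endpoint. The end-of-treatment, CGIC-only and per-protocol analyses use the same model. The supplementary Cochran-Armitage test has no stratification stated.

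Protocol 13.6.3 covers three global-impression endpoints in one sentence without covariates: "SGIC-SD/CGIC-SD, SGIC/CGIC and PGIC assessments recorded at the end of treatment will be analyzed with ordinal logistic regression using the proportional odds model".

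The endpoint is tests 5 (25 mg/kg/day) and 7 (50 mg/kg/day) in SAP Table 3, at two-sided 0.05. The sequence rule in SAP 5.5.1 is: "If a null hypothesis is not rejected then testing will stop and all subsequent analyses will be declared not statistically significant".

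**The concern.** An analysis would normally reflect the factors used to restrict the randomization. Here the one model that departs from this is alpha-controlled, while exploratory ordinal models in the same SAP follow it. The type of outcome does not explain the difference, because the seizure-duration rating is also a change rating against a Visit 3 memory aid.

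When arms are balanced within prognostic strata and the strata are left out, two things follow. The model standard error exceeds the estimator's real sampling variability, so the actual type I error falls below 5%. The arm-only (marginal) odds ratio is also nearer 1 than the age-conditional one. Both reduce the chance of rejecting. A failure at test 5 also closes off total seizures at 25 mg/kg/day and both remaining tests at 50 mg/kg/day.

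**Working it through.** **1. Handling of age across the plan**

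| Analysis | SAP section | Age group |
|---|---|---|
| Tests 1, 3: primary | 5.5.2 | in model |
| Tests 2, 4: 50% responders | 5.5.3.1.1 | CMH stratified by age |
| **Tests 5, 7: CGIC/SGIC** | **5.5.3.1.2** | **absent** |
| Tests 6, 8: total seizures | 5.5.3.1.3, as primary | in model |
| PGIC (outside hierarchy) | 5.5.3.2.6 | absent |
| Seizure-duration rating (exploratory) | 5.5.4.5 | "Proportional odd modelling will be carried out by including treatment arm and age group as factors" |
| Vineland-II levels (exploratory) | 5.5.4.6 | "Factors for treatment and age group will be included along with the baseline adaptive level as a covariate" |
| Responder logistic models | 5.5.5 | "will be modelled using logistic regression, including stratified age group and treatment arm as covariates" |

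**2. The plan's own power figure**

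The documents give power only for percentage change in seizures (SAP 3.2: "this sample size of 70 patients per arm", 90%, means 15% and 50%, SD 60%). By Noether's formula, p = Φ(35/(60√2)) = 0.660. Total N for two arms = (1.960 + 1.282)²/(12 × 0.25 × 0.160²) = 136.8, or 68.4 per arm. Power at 70 per arm is 90.6%, so the stated figure reproduces. There is no equivalent figure for CGIC/SGIC.

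**3. Simulation of the CGIC/SGIC test**

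From the documents: three arms of 70, four strata, seven categories, two-sided 0.05. Assumed: near-equal strata (18/17/18/17 per arm), placebo ratings 5/10/25/45/10/4/1%, age-conditional odds ratio 2.0 at both doses, equally spaced age effects. Each setting had 20,000 runs with a Wald test of 25 mg/kg/day against placebo. An age log-odds range R corresponds to a youngest-to-oldest odds ratio of exp(R).

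| R | exp(R) | Power, arm only | Power, arm + age | Difference (points) | Type I error, arm only |
|---|---|---|---|---|---|
| 0 | 1.0 | 61.0% | 61.6% | 0.6 | 5.1% |
| 0.5 | 1.6 | 60.8% | 61.8% | 1.0 | 4.8% |
| 1.0 | 2.7 | 59.6% | 62.1% | 2.5 | 4.8% |
| 1.5 | 4.5 | 57.1% | 61.9% | 4.8 | 4.4% |
| 2.0 | 7.4 | 53.4% | 61.5% | 8.1 | 3.7% |
| 3.0 | 20.1 | 46.2% | 62.2% | 16.0 | 2.2% |

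Type I error of the adjusted model is 5.1–5.6% throughout. With odds ratio 2.5 the loss is 0.4–1.7 points up to R = 1.0, 3–5 at 1.5–2.0 and 13 at 3.0. At R = 2.0, unequal strata (25/20/15/10 per arm) give 54.8 vs 61.5%, and flatter placebo ratings (3/12/20/30/20/10/5%) give 56.1 vs 64.4%.

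**4. Where the loss comes from (odds ratio 2.0, R = 2.0)**

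- Arm only: mean log-OR 0.63, model SE 0.309, sampling SD 0.288. Power ≈ Φ((0.63 − 1.96 × 0.309)/0.288) = Φ(0.085) = 53.4%.
- Arm + age: mean log-OR 0.70, model SE 0.313, sampling SD 0.317. Power ≈ Φ((0.70 − 1.96 × 0.313)/0.317) = Φ(0.273) = 60.8%.

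The reported SE does not fall when age is added. The gain comes from the larger log-OR.

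**5. Second simulation under different assumptions**

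Permuted blocks of 6 within four equally likely strata, placebo ratings 6/12/22/36/12/7/5%, odds ratio 2.5, 10,000 runs. The age effect is expressed as the between-stratum SD; for equally spaced strata SD = R × √1.25/3, so R = 2.0 is SD 0.75.

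| Age SD | Type I error, arm only | Power, arm only | Power, arm + age |
|---|---|---|---|
| 0 | 5.0% | 85.8% | 86.1% |
| 0.25 | 4.9% | 85.7% | 86.5% |
| 0.5 | 4.0% | 83.5% | 86.3% |
| 0.75 | 3.5% | 81.1% | 86.4% |
| 1.0 | 2.7% | 76.7% | 86.6% |
| 1.5 | 1.4% | 62.7% | 85.7% |

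Under the null at SD 0.75 the arm-only SE is 0.301 against a sampling SD of 0.281. The implied type I error is 2Φ(−1.96 × 0.301/0.281) = 2Φ(−2.10) = 3.6%, matching the simulated 3.5%. Adjusted type I error is 5.1–5.9%.

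**The case against.** The SAP follows the protocol. Protocol 13.6.3 names age group for the CMH test and the ANCOVA models but gives the global-impression models no covariates, so the SAP's departure is arguably the seizure-duration model. An arm-only odds ratio is a valid marginal estimate. Nothing in the documents shows that age predicts a rating made against the patient's own Visit 3 condition. The larger losses need strong age effects: R = 2.0 means an odds ratio of 7.4 between youngest and oldest, far above the assumed drug effect. Some of the small-range difference is not due to age, since 0.6 points appear at R = 0. The adjusted test runs slightly above nominal. Test 5 is reached only after both doses have won on the primary and responder tests, and the power figures here do not condition on that.

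Most of this stands as limits on size: there is no validity error, the loss is small for weak age effects, and the power figures are standalone. It does not explain why the protocol's single sentence became two different models, with the gated endpoint getting the weaker one. The protocol's silence on covariates does not forbid age group, as the SAP's own seizure-duration model shows.

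**Conclusion.** The point holds. Of the eight gated tests, only 5 and 7 ignore the randomization strata, and no reason is given. If age is prognostic and the schedule balances arms within strata, the planned test is conservative and its odds ratio is pulled towards 1. At an assumed odds ratio of 2.0 to 2.5, the first simulation's loss is about 0.4–2.5 points up to R = 1.0, 3–8 points at 1.5–2.0 and 13–16 at 3.0. If age is not prognostic, nothing is lost either way. The rating distribution, odds ratios, age effects, stratum sizes and block size are assumptions; two simulations with different choices agree on direction and closely on size. This is a change that should be made for efficiency and consistency, not a threat to the type I error. PGIC is affected for consistency only.

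**What to change.** Before unblinding, specify treatment arm and stratified age group as factors in the proportional odds model of SAP 5.5.3.1.2 (last-visit, end-of-treatment and CGIC-only versions) and of 5.5.3.2.6, and state that the odds ratio is conditional on age group. This brings both into line with 5.5.4.5. Keep the arm-only odds ratio as a sensitivity analysis. Replace the supplementary trend test with its age-stratified form, the 1-df Cochran-Mantel-Haenszel correlation test. If the omission is deliberate, one sentence giving the reason, for example in SAP 5.8, is enough.

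The cost is one phrase in each of two sections and 3 model degrees of freedom, with no power loss if age has no effect (61.0 vs 61.6%). There are two small downsides. Adjusted type I error was 5.1–5.9% across the simulations. The proportional-odds score test goes from 5 × 2 = 10 to 5 × 5 = 25 degrees of freedom, and when proportional odds holds its rate of p < 0.05 moves from 4.2–4.5% to 4.3–6.8% (odds ratio 2.0, R from 0 to 3.0). A trigger only adds the supplementary analysis.
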